## 8. Responses to **Qualitative Interview**

### Sample Size Calculations

We will compile data from qualitative interviews, and summarize key points about the intervention brought up by patients. This report will further guide development and refinement of the inpatient VR intervention.

We will also examine changes in scores on patient-reported pain, blood pressure and pulse rate. We will compute change scores for each of these measures and also compare these patients to the Control group. If data are normally distributed, we will use a paired Student's t test for comparisons pre- and post-intervention, and two-sample t tests for between group comparisons. If data are abnormally skewed, we will conduct similar analyses using the non-parametric Wilcoxon signed-rank test, and the Wilcoxon rank-sum test, respectively.

We are uncertain of the degree of change we will observe in patient responses to the Quantitative Patient Survey (PROMIS + CSEI), pain ratings, and cardiac vitals after exposure to the VR intervention, as a study of this type has not been previously conducted.

We have decided instead to use established, clinically-meaningful changes in pain ratings as a means of estimating change. Previous studies have shown that for the minimum clinically important difference in pain scores varies by baseline starting pain level. For those subjects starting with a baseline pain level of 40-70 mm (as in our planned cohort), the minimum clinically important difference is 13 mm (Olsen, BMC Medicine 2017).

For all analyses, we will assume a 5% Type I error rate (alpha) and a 20% type II error rate (or 80% power). If we assume that the baseline median pain level of our patients is 55 mm, then for within group analyses to show a 13 mm reduction in pain would require 20 patients in each arm for 40 patients total.

Therefore, to conduct one RCT of the effect of VR on pain starting at a median level of 55 mm, we would need 40 patients:

[Control (20 patients)]

[VR (20 patients)]

We will also perform between group analyses, we will compare pain scores obtained from all inpatients exposed to the VR intervention to the Control. Our calculated sample size will also be adequate to identify a difference between groups.

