### Pre-Intervention Procedures

The study staff member will arrive at bedside, explain the risks and benefits of the study, and will obtain informed consent. Next, a physician or authorized study staff member will collect blood pressure and pulse data using standard sphygmomanometers in hospital wards, and will ask the patient to report current pain level on a 0 to 10 scale. We will also assess coping (Roberts, 2010) by asking "How are you coping with your labor?" We will also obtain all pain ratings collected and documented in the EHR during the current hospitalization up to 96 hours

before the intervention. Additionally, the study staff member will administer the **Quantitative Patient Survey** -- included at the end of this document and based on the NIH PROMIS Global Health Survey (10 items) and Childbirth Self-Efficacy inventory (15 items).

When a patient expresses interest in the study, she will then undergo randomization to either the VR arm or the Control arm of the study. Group assignments will be maintained inside sequentially numbered, sealed, opaque envelopes. After informed consent, study personnel will then open the assigned envelope and the study treatment will be revealed. Patients, providers, and study personnel will not be blinded to the assigned intervention.

For those patients randomized to VR, the study staff member will explain the use of the Samsung VR goggle set, and thereafter will allow the patient to use the device freely for up to 30 minutes. Intervals of 2-5 minutes is suggested for first-time use, and patients will be to allowed to discontinue it at any time as long as they are not experiencing any discomfort or side effects (dizziness, motion sickness, etc.). The study staff member will be present at all times, and will work with hospital staff as necessary to ensure the patient is receiving appropriate clinical care throughout the duration of the intervention.

For those patients randomized to the Control, the study staff member will explain that their assignment has been to the standard of care for which is no specific dedicated intervention at this time. Rather their intervention will only be further assessment of their pain scores, vitals, and medication use.

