### **Outcomes and Data Collection**

Primary Outcome: Reduction in pain scores from pre- to post-intervention

Secondary Outcome:

1. Duration of use of the intervention
2. Acceptability of the intervention
3. Need for IV pain medication during the intervention
  - a. Time to IV pain medication after the intervention
4. Request for an epidural during the intervention
  - a. Time to epidural use after the intervention
5. Vital sign changes during and after the intervention including heart rate and blood pressure.

Data Collection

1. Baseline maternal demographics
  - a. Name and Medical Record Number (secured and stored separate from all other data below)
  - b. Age
  - c. Race/Ethnicity
  - d. Insurance status
  - e. Gravidity/Parity
2. Admitting diagnosis
3. Obstetric data
  - a. Gestational age
  - b. Induction agents
  - c. Mode of delivery
4. Vital Signs (blood pressure, heart rate) before, during (continuous pulse oximeter and blood pressure measurements every 10 minutes) and after the intervention.
5. Pain scores before and after the intervention. Average Pain Rating during 4 hours before intervention, and Average Pain Rating after intervention (up to 24 hours).
6. Pain interventions including time to first use of IV pain medication and first use of epidural.
7. Responses to **Quantitative Patient Survey** (PROMIS Global Health pre-intervention, and modified Childbirth Self-Efficacy Inventory pre- and post-intervention)

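### The between-arm pain comparison does not adjust for baseline pain; pre-specifying the adjustment costs almost nothing and guards against chance imbalance, though the precision gain is uncertain and often modest

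*Combined protocol and SAP*

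**What the plan says.** The Outcomes and Data Collection section defines "Primary Outcome: Reduction in pain scores from pre- to post-intervention". The analysis is described under Sample Size Calculations. There the plan says "We will compute change scores for each of these measures and also compare these patients to the Control group". For roughly normal data, the tests are named as follows: "we will use a paired Student's t test for comparisons pre- and post-intervention, and two-sample t tests for between group comparisons". Skewness triggers a fallback: "we will conduct similar analyses using the non-parametric Wilcoxon signed-rank test, and the Wilcoxon rank-sum test, respectively". None of these tests carries a covariate.

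A later sentence in the same section describes the between-arm analysis again: "we will compare pain scores obtained from all inpatients exposed to the VR intervention to the Control". It does not say whether the scores are changes or post-session values. Read either way, it is unadjusted.

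Baseline pain is available. Under Pre-Intervention Procedures, study staff "will ask the patient to report current pain level on a 0 to 10 scale", and the data collection list includes "Pain scores before and after the intervention". Entry is restricted to ratings of 4 to 7. Allocation is by sequentially numbered sealed envelopes, 20 women per arm, and no stratification by baseline pain is described.

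**The concern.** Comparing change scores amounts to assuming that each extra millimetre of pre-session pain predicts one extra millimetre of post-session pain. If the true slope is lower, subtracting the whole baseline has two effects:

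- It adds noise to the comparison.
- It over-corrects any chance difference in baseline pain, and so flatters the arm that started with more pain.

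A slope below 1 is a reasonable expectation here. The outcome is a single rating of contraction pain, repeated after a session of up to 30 minutes, and the section justifying record review for recruitment itself remarks on how quickly pain scores and contraction readings change. With 20 women per arm, chance imbalance can be sizeable and precision is scarce. The baseline rating that would deal with both is already being collected.

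**Working it through.** **Inputs from the plan.** 20 per arm; 5% alpha (sidedness not stated, two-sided assumed); 80% power; 13 mm difference; entry ratings 4 to 7. I take 1 rating point as 10 mm.

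**The plan's own figure.** The 20 per arm was derived for a within-group 13 mm reduction, but no SD is given, so it cannot be reproduced forward. Solving the paired t test (n = 20, 19 df, two-sided 5%, 80% power) gives a standardised effect of 0.660. The implied SD of change is 13 / 0.660 = 19.7 mm, with variance 387.5. A one-sided test would imply 22.5 mm.

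**Unadjusted between-arm power.** The standard error is 19.7 × √(2/20) = 6.22 mm. The noncentrality is 13 / 6.22 = 2.09 on 38 df, and power is 53.0%.

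**Baseline SD (assumed).** Ratings spread evenly over 40, 50, 60 and 70 mm have variance (15² + 5² + 5² + 15²)/4 = 125, so SD 11.2 mm.

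**Adjusted analysis.** Let b be the slope of post-session on pre-session pain. The residual variance is 387.5 − (1 − b)² × 125. Estimating the slope with 40 women inflates the variance of the arm effect by about 1 + 1/36 and uses one degree of freedom (37 remain). Effective size is 20 divided by the variance ratio.

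| Slope b | Residual variance | Ratio to 387.5, with inflation | Effective women per arm | Power at 13 mm |
|---|---|---|---|---|
| 0.2 | 307.5 | 0.816 | 24.5 | 61.5% |
| 0.3 | 326.2 | 0.865 | 23.1 | 59.0% |
| 0.5 | 356.2 | 0.945 | 21.2 | 55.3% |
| 0.7 | 376.2 | 0.998 | 20.0 | 53.0% |
| 1.0 | 387.5 | 1.028 | 19.5 | 51.9% |

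**Sensitivity to baseline spread.** If ratings cluster near the assumed 55 mm median, with an SD of 8 mm (variance 64), the same steps give 56.4% at slope 0.2 and 52.5% at slope 0.7.

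**Chance imbalance.** With a baseline SD of 11.2 mm, the baseline difference between arms has standard error 11.2 × √(2/20) = 3.5 mm. A difference of 5 mm or more, in either direction, is 1.41 standard errors and occurs in about 16% of randomisations. The change-score estimate keeps (1 − b) times the imbalance:

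- at b = 0.2, 0.8 × 5 = 4 mm, or 31% of the 13 mm target;
- at b = 0.7, 0.3 × 5 = 1.5 mm, or 12%.

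**The case against.** The strongest reply is that nothing here is an error. Under randomisation the change-score comparison is unbiased on average, its type I error is correct, and it matches the stated primary outcome. All of that stands. A reader might infer that the planned test is biased or invalid; the documents do not support that. The imbalance effect is conditional on the sample actually drawn.

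A second reply is that the slope is unknown. This also stands. It is tempting to argue that the 4-to-7 entry window forces the slope below 1, but truncating a predictor does not lower a linear slope. The window narrows the baseline spread, which makes adjustment less useful. The expectation of a lower slope rests only on the variability of single ratings.

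A third reply is that the usual efficiency argument is asymptotic. Without the inflation term, the powers at slopes 0.2, 0.3, 0.5 and 0.7 would be 62.7%, 60.1%, 56.4% and 54.2%, which overstates the gain with 40 women. The familiar variance ratio (1 + ρ)/2, for equal pre- and post-session SDs, would suggest more still (70% power at ρ = 0.3). Combined with a 19.7 mm change SD, it needs a baseline SD of 19.7 / √(2 × 0.7) = 16.6 mm. Ratings confined to 40–70 mm cannot exceed an SD of 15 mm.

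The outcome definition is no obstacle. With pre-session pain in the model, regressing post-session pain or change on arm gives the same arm coefficient.

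**Conclusion.** The point holds as a recommended improvement in precision and in protection against chance imbalance; it does not correct an invalid test. On the stated assumptions, adjustment is worth up to about 8.5 points of power at a slope of 0.2 (61.5% against 53.0%), about 2 points at 0.5 and nothing from about 0.7. At slope 1 it costs about 1 point. Gains are smaller if baseline ratings cluster. The imbalance protection is worth 1.5 to 4 mm per 5 mm of baseline difference over slopes 0.7 to 0.2.

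These sizes rest on a back-solved change SD, an assumed baseline SD, two-sided testing and a range of slopes, none of which the documents supply.

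A reader might also infer that adjustment makes 20 per arm enough for the between-arm comparison. It does not: every power in the table is well below 80%. The plan's sizing on a within-group change is a separate and larger matter.

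**What to change.** In the analysis paragraph of Sample Size Calculations, pre-specify one between-arm pain analysis: linear regression of post-session pain (or, equivalently, change) on assigned arm, with pre-session pain as covariate, reporting the adjusted mean difference and its 95% confidence interval. Keep the rank-sum test as a sensitivity analysis. Bring the later sentence on comparing pain scores into line, so that only one analysis is described. State the SD and pre–post correlation assumed. The same model may be used for blood pressure and pulse, though no gain has been calculated for them.

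The cost is a sentence or two of text, one degree of freedom and, at worst, about one point of power. No new data are needed.

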### **Study Procedures**

This protocol is a randomized controlled trial of patients in labor at Cedars-Sinai Hospital.

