#### Subject Participation End

The subject's participation will be completed when they wish to discontinue either intervention or at 30 minutes.

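### The between-group comparison is worded as women exposed to VR versus Control, not as women assigned to each arm, which can bias the randomised comparison in either direction

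*Combined protocol and SAP*

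**What the plan says.** Study Procedures sets the design: "This protocol is a randomized controlled trial of patients in labor at Cedars-Sinai Hospital". Study Population and Period plans 20 women per arm. Under Pre-Intervention Procedures, assignment becomes known before any headset use: "After informed consent, study personnel will then open the assigned envelope and the study treatment will be revealed". The trial is open: "Patients, providers, and study personnel will not be blinded to the assigned intervention". Use of the headset is voluntary and no minimum is set. Subject Participation End adds that "participation will be completed when they wish to discontinue either intervention or at 30 minutes".

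The primary outcome (Outcomes and Data Collection) is the fall in pain score from before to after the intervention. Sample Size Calculations mentions the between-arm comparison in three places:

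- "We will compute change scores for each of these measures and also compare these patients to the Control group", with no analysis set named.
- "two-sample t tests for between group comparisons", or a rank-sum test if the data are skewed, again with no analysis set named.
- "we will compare pain scores obtained from all inpatients exposed to the VR intervention to the Control". This is the only one that says who is counted on the VR side.

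The document does not mention intention-to-treat, define an analysis population, define *exposed*, or say what happens to a woman assigned to VR who never puts the headset on.

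**The concern.** Randomisation makes the arms comparable only if women are counted where they were assigned. Taken literally, the quoted sentence defines the VR side by something that happens after the envelope is opened and leaves the Control side unrestricted. A woman in the VR arm who declines the headset, or chooses other pain relief first, would leave the comparison. A woman with the same course in Control would stay, because Control has no exposure to miss.

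The comparison affected is the one that matters most. Background hypothesises that VR reduces pain more than no intervention, and only the between-group test addresses that; the paired tests within each arm cannot. With 20 per arm, each woman lost is 5% of her arm. In an open trial, an undefined exposure criterion also leaves room to settle the analysis set after outcomes are known.

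**Working it through.** **1. Can non-exposure occur?** Yes. Assignment is revealed before use, and use is voluntary. Other pain management is unrestricted (How the research differs from Standard of Care). Post-Intervention Procedures times the post score at completion of the intervention, so a woman who never starts VR has no defined scoring time and could drop out of the data by default. The document gives no expected number of non-users.

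**2. Inputs.** From Sample Size Calculations: 13 mm target, 5% alpha, 80% power, 20 per arm, based on the within-group change. No SD is stated, so the 20 cannot be reproduced directly. Solving for the SD of change that yields n = 20:

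- Two-sided normal: SD = 13 × √20 / (1.96 + 0.84) ≈ 20.8 mm.
- Two-sided paired t test (noncentral t): 19.7 mm.
- One-sided normal: 23.4 mm.

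I use 19.7 mm below. Bias in mm scales in proportion to the SD.

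**3. Bias formula.** Assume no VR effect and normally distributed change scores. Let the k VR women ranked worst on a trait having correlation ρ with their pain reduction be the ones never exposed. Then

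bias = ρ × SD × (sum of the k largest expected normal order statistics for n = 20) / (20 − k).

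The first three order statistics are 1.87, 1.41 and 1.13, with sums 1.87, 3.28 and 4.41. At ρ = 1:

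- k = 1: 19.7 × 1.87 / 19 = 1.9 mm
- k = 2: 19.7 × 3.28 / 18 = 3.6 mm
- k = 3: 19.7 × 4.41 / 17 = 5.1 mm

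At ρ = 0.5 these halve to 1.0, 1.8 and 2.6 mm. At ρ = −0.5 they have the same size and run against VR. At ρ = 0 the bias is zero.

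**4. False positives.** Simulated trials with no VR effect and a two-sided 5% two-sample t test; the nominal rate favouring VR is 2.5%. Repeat runs differ by about 0.3 of a percentage point.

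| Correlation | Bias, k = 1 to 3 | False positives favouring VR |
|---|---|---|
| +1 (upper bound) | +1.9 to +5.1 mm | 5.5 to 13.8% |
| +0.5 | +1.0 to +2.6 mm | 3.7 to 6.2% |
| 0 | 0 | about 2.5% |
| −0.5 | −1.0 to −2.6 mm | 1.7 to 1.0% |

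**5. Cross-check by another route.** If a share p of the VR arm is dropped and those women would have had a pain reduction poorer by g mm, the bias is p × g. With 2 of 20 dropped and g = 10 or 20 mm, it is 0.10 × 10 = 1 mm or 0.10 × 20 = 2 mm. With 4 of 20 it is 2 or 4 mm. The sign reverses when g is negative. In simulations on this basis (SD 15 and 20 mm), the comparison by assigned arm kept its two-sided error at about 4 to 5% throughout.

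**The case against.** The strongest reply is that *exposed* is loose wording for *assigned*. Background uses the word as a cohort label for the institution's previous comparative study, on which this trial is modelled, and no sentence states that non-users will be excluded. That is a fair reading, and it makes this an ambiguous rule rather than a declared per-protocol analysis. But the only sentence that names the VR group names it by exposure, and nothing elsewhere restores analysis by assignment.

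Second, few women may be affected. Recruits have shown interest, staff introduce the headset at the bedside, and a woman who starts and stops early is still exposed. This stands: the number lost could be zero. The rule on ending participation also covers Control, so early endings are not confined to VR, although the exposure condition is.

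Third, the trial is sized on within-group change, and the between-group test is introduced as an additional analysis and not designated primary. That is true of the text, but it remains the only test of the hypothesis that VR beats no intervention.

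A reader might go further and infer that the wording biases the result toward VR. The documents do not support that. It requires non-users to have a worse pain change, which is nowhere established. With other analgesia unrestricted, a woman whose pain escalates before she uses the headset may be treated and report a low post score; dropping her would count against VR. So would dropping a woman with a milder course who declines.

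**Conclusion.** The point holds as a defect in the analysis set, not as a demonstrated bias toward VR. Read literally, the plan removes never-exposed women from one arm only, using a status decided after randomisation and left undefined. The bias can take either sign or be nil. In the illustration, a correlation of 0.5 in size gives 8% to 20% of the 13 mm target (1.0/13 to 2.6/13). The upper bound of 5.1 mm, or 39% of the target, requires the non-users to be exactly the women with the worst change scores and should not be read as the expected size. All of these figures rest on an assumed 1 to 3 non-users, an assumed selection strength and a back-solved SD, none of which the documents supply.

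**What to change.** Replace the sentence in Sample Size Calculations with: *The between-group analysis compares all women randomised to VR with all women randomised to Control, by assigned arm, whether or not and for however long the headset was used.*

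In Post-Intervention Procedures, require the post-intervention pain score from every randomised woman at a time defined the same way in both arms, including women who never start VR, and reconcile this with Subject Participation End. State how any score still missing is handled. If an exposed-only comparison is wanted, define *exposed* and label that comparison supportive.

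The cost is a wording change plus a small procedural addition to time the score in non-users. The estimated effect may be smaller: if VR gave 13 mm in users and nothing in non-users, 2 non-users of 20 would reduce the expected difference to 13 × 18/20 = 11.7 mm. The planned N stays at 40.

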### Study Population and Period

The study population will consist of 40 patients: 20 in the VR arm and 20 in the Control arm (see below for sample size calculations).

We anticipate the recruitment and intervention portion of the study to be completed within 12 months.

The Inclusion criteria are as follows:

1. Female
2. >18 years old
3. English-speaking
4. Able to understand the goals of the study and provide informed consent
5. Pregnant with term gestation
6. Nullipara
7. Pain due to contractions rated from 4-7
8. Contractions at least every 5 minutes x 30 minutes preceding

The Exclusion criteria are as follows:

1. Parous
2. Use of medications for pain relief prior to the intervention
3. Use of an epidural
4. Preterm gestation
5. Pain not due to contractions
6. Pain score of 3 or below or 8 or above
7. Preeclampsia with severe features, eclampsia
8. History of epilepsy, dementia, or other neurologic disease that would prevent using VR
9. Sensitivity to flashing light / motion
10. Medical condition predisposing to nausea or dizziness
11. Injury to the eyes, face, neck, or arms that prevents comfortable use of VR hardware or software, or safe use of the hardware (e.g., open sores, wounds, or skin rash on face)

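### The 20 per arm was derived for a within-arm test; on the plan's own figures it gives about 53% power for the between-arm comparison that it is said to support.

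*Combined protocol and SAP*

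**What the plan says.** All the relevant statements on size are in the Sample Size Calculations section, except the allocation, which is under Study Population and Period ("20 in the VR arm and 20 in the Control arm").

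- Error rates are set once, for every analysis: 5% type I error and "a 20% type II error rate (or 80% power").
- The only effect size is taken from published work on pain scores. For baseline pain of 40 to 70 mm, "the minimum clinically important difference is 13 mm".
- The only derivation is for the pre-post comparison. It assumes a baseline median of 55 mm and reads: "then for within group analyses to show a 13 mm reduction in pain would require 20 patients in each arm for 40 patients total".
- The between-arm claim closes the section: "Our calculated sample size will also be adequate to identify a difference between groups".

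The same section plans paired t tests for pre-post comparisons and two-sample t tests between arms, with Wilcoxon tests as the fallback for skewed data. It gives no SD, no separate between-arm difference, no sidedness and no dropout allowance.

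**The concern.** The two tests do not have the same precision. With equal SDs and 20 per arm, the variance of a difference between two mean changes is twice that of one mean change, so the standard error is larger by a factor of √2. A size that is just enough for the paired test is too small for the two-sample test at the same difference.

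The Background section hypothesises that VR reduces pain more than no intervention does, and the design is a randomised controlled trial. Only the between-arm contrast tests that hypothesis. A fall within the VR arm cannot be separated from the effect of time, or from regression to the mean after enrolling only women with pain scores of 4 to 7. If readers accept the adequacy statement, they may take a non-significant result as evidence against VR, although the trial had roughly an even chance of detecting the plan's own clinically important difference.

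**Working it through.** **Inputs from the plan:** 20 per arm; 13 mm; alpha 5%; power 80%; paired t test within arm; two-sample t test between arms. **Assumptions:** two-sided tests; 13 mm is also the between-arm difference in change; equal SDs in the two arms; no dropout.

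**Step 1. The plan's own figure.** The 20 cannot be reproduced directly because no SD is stated, so I solved for the SD that makes it true. The baseline median of 55 mm serves only to select the 13 mm; it does not enter the paired formula.

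Paired test: noncentrality = (13/SD) × √n, with n − 1 = 19 degrees of freedom. Power is 80% at n = 20 when 13/SD = 0.660, so

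SD of change = 13 / 0.660 = 19.7 mm.

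If 20 is the rounded-up minimum, the SD lies between 19.1 mm (n = 19 just sufficient) and 19.7 mm. With the normal approximation, 13/SD = (1.960 + 0.842)/√20 = 0.626, so the SD is 20.8 mm.

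**Step 2. The same ratio in the two-sample test.** Noncentrality = (13/SD) × √(n/2), with 2n − 2 = 38 degrees of freedom.

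- Paired: 0.660 × √20 = 2.95, giving power 80%.
- Two-sample: 0.660 × √10 = 2.09, giving power 53.0%.

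| Basis for the SD | SD of change | Between-arm power for 13 mm, 20 per arm |
|---|---|---|
| n = 19 boundary | 19.1 mm | 55% |
| n = 20 exact, paired t | 19.7 mm | 53% |
| Normal approximation | 20.8 mm | 49% |

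**Step 3. What 20 per arm can do at SD 19.7 mm.**

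- The two-sample test has 80% power at a standardised difference of 0.909, so the detectable difference is 0.909 × 19.68 = 17.9 mm, or 17.9/13 = 1.4 times the 13 mm.
- Expected half-width of the 95% confidence interval: 2.024 × 19.68 × √(2/20) = 12.6 mm, almost the whole 13 mm.
- For 80% power at 13 mm: 36 per arm gives 78.9% and 37 per arm gives 80.0%.

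**Step 4. Could a smaller SD rescue the claim?** For 80% between-arm power at 13 mm, the SD must be no more than 13/0.909 = 14.3 mm. At that SD the paired test needs 12 patients, not 20.

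**Step 5. One-sided planning.** If the 20 came from a one-sided 5% paired test, the implied SD is 22.5 mm. Between-arm power is then 56% one-sided, or 43% if the test is two-sided.

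**The case against.** The strongest reply is that 53% is conditional. The plan states no SD, and 20 may not be the exact minimum. If the paired calculation gave a smaller number that was then padded to 20 (an assumption; the plan does not say so), between-arm power would be 58% from a minimum of 18, 64% from 16 and 78% from 12. These lie outside the 49% to 55% range, so that range covers rounding and approximation only. All of them are still below 80%. At an SD of 14.3 mm or less, 20 per arm would serve both tests, and the conflict disappears if the stated requirement of 20 is read as generous rather than as a minimum. That is not its natural reading.

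The closing paragraph also speaks of comparing pain scores, not change scores. If post-intervention scores were compared, with equal pre and post SDs and the same implied SD of change, power would be 82%, 67%, 53% and 35% at pre-post correlations of 0, 0.3, 0.5 and 0.7. It passes 80% only near zero correlation. The primary outcome (reduction from pre to post) and the planned change scores point to the change-score reading. Baseline adjustment is not planned; it would give about 71%, 65% and 60% at correlations of 0.3, 0.5 and 0.7.

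Finally, the disputed sentence itself names neither 13 mm nor 80%. But the section sets its error rates for all analyses and offers no other effect size.

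What stands is that the 53% must be reported with its conditions, and that 19.7 mm is an implied value, not one the plan adopted.

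**Conclusion.** The concern holds. The adequacy statement has no calculation behind it and does not fit the section's own derivation. Taking 20 as the minimum for a two-sided paired test of 13 mm at 80% power, with the same 13 mm between arms, equal SDs, change scores and no dropout, between-arm power is about 53% (49% to 55%). The difference detectable with 80% power is 17.9 mm, and 13 mm would need about 37 per arm. Any dropout lowers the power further. None of the padded sizes examined brings it to 80%. The claim survives only with an unstated SD of 14.3 mm or less, which would make the within-arm requirement of 20 wrong, or with post-intervention scores almost uncorrelated with baseline. This must be corrected because it misdescribes the comparison on which the trial's hypothesis rests.

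**What to change.** In Sample Size Calculations:

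1. Delete the sentence on between-group adequacy.
2. Limit the 80% power statement to the within-arm test.
3. State the SD of change that was assumed, with its source, and say whether the test is two-sided. If the sponsor has no SD of its own, give a range and label any back-solved value as such.
4. Give the between-arm figures for change scores. For example: with 20 per arm and an SD of change of 19.7 mm (implied by the within-arm calculation), the between-arm comparison has about 53% power for 13 mm and 80% power for 17.9 mm.

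The trial stays at 40 patients. The cost is a few sentences and a less favourable stated power.
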